The Effect of Tablet Size on Cognitive Performance:

A Randomized Control Trial Using Caffeine

[name]

University of Colorado Denver

[name]

[name]

[name]

July 9, 2018

Abstract

Background: A capsule's physical design (e.g. shape, size, and color) affects individuals' perception of drug efficacy; that is, how well a drug is likely to work. The goal of this study is to assess the effects tablet size may have on participant's performance on cognitive testing since research has found differences between preparation methods. **Method:** 120 participants will be randomly assigned to one of four groups: 1) 90 mg caffeine with a 1 mm diameter sucrose pillule; 2) no caffeine with the small sucrose pillule; 3) 90 mg caffeine with a 5 mm sucrose pillule; 4) no caffeine with the large sucrose pillule. Participants will consume the designated placebo tablet with water (caffeinated or non-caffeinated); then, participants will provide weekly caffeine intake and complete the neutral portion of Velten's Mood Induction Procedure until 30 minutes have passed to allow for caffeine activation. Participants will complete the Stroop test, Trial Making Tests A and B, and the Rey Auditory Verbal Learning Test. Previous literature, as far as the author knows, relied on evaluating drug efficacy based on appearance alone. This study aims to assess if tablet size, due to placebo effect, alters participants' performance on cognitive tests after consuming caffeinee. The Effect of Tablet Size on Cognitive Performance:

A Randomized Control Trial Using Caffeine

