Previous research relied heavily on participants' perceptions to rate a drug's effectiveness and purpose; this study was designed with randomized, placebo-controlled trials to evaluate the main goal using objective quantitative data. I will use neuropsychological testing to assess if tablet size affects participants' short-term memory, executive function, and processing speed using caffeine as the drug of choice. Previous research has supported a significant cognitive boost in these cognitive functions for caffeine dosages of at least 75 mg (EFSA, 2011). If tablet size affects perceptions of how effective a dose of caffeine will be, despite doses remaining constant in the caffeinated groups, then I expect significant differences among the two tablet sizes for processing speed, executive functioning, and memory capabilities in participants. This study may prove foundational to better understanding more effective physical drug designs.

Hypotheses

There are three hypotheses for this experiment:

- caffeine will significantly improve participant's memory, executive function, and processing speed;
- there will be a significant difference in participant performance associated with tablet size;
- 3) there will be an interaction effect between caffeine content and tablet size.

Method

Participants

120 participants, primarily Psychology students fulfilling a research participation requirement for Introduction to Psychology courses, will be recruited. Ambulatory participants that are fluent in written and spoken English will be used because they should be able to complete the neuropsychological tests.

Participants that are allergic to sucrose and/or caffeine will be excluded because they are essential components to the procedure. Participants with cardiovascular disease or uncontrolled high blood pressure will be excluded because the use of caffeine may exacerbate these conditions. Participants with untreated or unresolved anxiety and/or depressive disorders will be excluded because caffeine may exacerbate symptoms related to these disorders as well. Participants that are pregnant will be excluded from this study. Lastly, participants that have a diagnosed learning disability will be excluded because the neuropsychological tests will only use scores normalized for the general population.

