This test asks participants to connect a series of numbers and letters that are randomly distributed on the test page. The goal of these tasks is to connect the series of numbers and letters in order (e.g. 1-A-2-B-3-C) as quickly as possible (Appendix C). Switching between alphabetic and numeric sets and timing completion times, in seconds, is an effective measure of executive functioning capabilities. Longer completion times indicate lower executive function capabilities because participants take longer to switch between sets. The Cronbach's alpha of Trail B is .88 (Smith, et al., 2008).

Memory.

Rey Auditory Verbal Learning Test (RAVLT).

Participants are presented with 15 unrelated words and asked to recall as many as they can over five trials. This section assesses immediate recall ability. An additional 15 unrelated words are then introduced as an interference component. Participants must recall as many of the original 15 words as possible after being presented with interference. Lastly, after an interval of 30 minutes, participants are asked to recall the original 15 words again (Appendix D). The trials are scored by counting the correct number of words recalled, the % recalled (the final delayed-recall trial(A7) divided by the final immediate recall trial (A5)), and the number of intrusions (i.e. the number of incorrect words). A higher percentage of recall with little to no intrusions are considered better memory. The Cronbach's alpha reliability of the Rey Auditory Verbal learning Test is .84 (Magalhaes, et al., 2012).

Procedure

Materials for this procedure will need to be prepared beforehand. 90 mg packets of caffeine will be prepared from 200 mg pure caffeine powder capsules by opening capsules and measuring out the desired weight of caffeine using a scale that can measure accurately to the thousandths gram. The weight of each prepared packet will be recorded by hand in a notebook until it is used in a trial. Before participants arrive, the prepared caffeine packet will be mixed with distilled water and one pillule of each size will be placed into small paper cups marked A and B.

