Procedures will be explained to participants at first contact, and they will sign an informed consent form to confirm eligibility (Figure 2). Participants will be randomly assigned to one of the four groups (Figure 1). Based on a power analysis conducted at 0.80 power on Pasman et al.'s work on the effects of caffeine in a home-setting, 120 participants will need to be recruited in this study to successfully detect any significant effect (Pasman et al., 2017).

Participants will be required to not have consumed caffeine the day of testing. Participants will be presented with 8 ounces of distilled water and the cups containing each sucrose placebo pill. They will be asked to drink the water and only one of the sucrose pillules (depending on the group they were placed in); half of the participants (n=60) will drink water mixed with 90 mg of dissolved caffeine (Figure 1). After consumption, participants will be asked to complete Velten's Neutral Mood Induction Procedure (Appendix A) until 30 minutes have passed to allow for caffeine activation in the body (Institute of Medicine (US) Committee on Military Nutrition Research, 2001). Participants will then begin with the series of Stroop tests. After completing the three Stroop tests, participants will complete the first section of the Rey Auditory Verbal Learning test (immediate recall). During the 30-minute waiting period

participants will complete Trail Making Tasks A and B, and fill out a demographic survey designed to collect: 1) their weekly caffeine intake using the Caffeine Consumption Questionnaire (Appendix E); 2) sex; 3) age; 4) ethnicity and race; 5) year in school (i.e. freshman, sophomore, etc.); 6) GPA; and 7) academic major. The time of day the trial begins will also be recorded. The data collected in the survey will be used to adjust scores during data analyses. If students are unable to complete the survey and caffeine questionnaire within the 30-minute waiting period allotted for the RAVLT, the survey materials will be set aside and completed after participants finish the second component of the RAVLT. After completing the second portion of the RAVLT participants will be debriefed, and the trial will conclude.

Data Analysis

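### Caffeine in plain distilled water is compared with plain distilled water and nothing matches the taste, so the drink can reveal the caffeine factor and mix expectancy into all three hypotheses

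*Combined protocol and SAP*

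**What the plan says.** The document is a combined protocol and SAP for a 2×2 trial of caffeine (90 mg or none) by sucrose pillule size (1 mm or 5 mm). The pillule is inert in all four groups, and the drug is in the drink.

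- Preparation (Procedure): "the prepared caffeine packet will be mixed with distilled water and one pillule of each size will be placed into small paper cups".
- Administration (Procedure): "Participants will be presented with 8 ounces of distilled water and the cups containing each sucrose placebo pill". Each participant swallows one of the two pillules, according to group, and "half of the participants (n=60) will drink water mixed with 90 mg of dissolved caffeine".
- Mechanism (Present Study): the prediction of a size difference begins "If tablet size affects perceptions of how effective a dose of caffeine will be, despite doses remaining constant in the caffeinated groups". The Abstract likewise attributes any size effect to placebo response.
- What participants may know: under Participants, "Participants that are allergic to sucrose and/or caffeine will be excluded because they are essential components to the procedure". Under Procedure, no caffeine may be taken on the day of testing, and "Procedures will be explained to participants at first contact, and they will sign an informed consent form to confirm eligibility". The participant information itself is not in the text available for this review.
- Analysis (Data Analysis): ANCOVAs if weekly caffeine consumption correlates with the scores, otherwise ANOVAs. The Procedure adds that survey data will be used for adjustment.

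The Procedure gives the precision of the scale and the marking of the cups. It names no flavouring, control additive, taste comparison or masking of participants, and no question on what participants think they received.

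**The concern.** The trial studies expectation, and the pillule is meant to carry it. The two drinks differ in composition in a way that may be tasted, and that difference coincides exactly with the caffeine factor. A participant who notices it has a reason to credit the drink instead of the pillule. Randomisation cannot remove a cue that is part of one factor. The planned ANOVA or ANCOVA cannot remove it either, because neither taste nor belief about treatment is recorded.

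All three hypotheses are exposed:

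- **Hypothesis 1 (caffeine):** the contrast becomes drug plus awareness of drug.
- **Hypothesis 2 (size):** the effect may be diluted among people who credit the drink.
- **Hypothesis 3 (interaction):** it may be biased if the size expectancy is weakened to different degrees in caffeine and plain-water groups.

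Only the caffeine factor is at risk of being revealed. Pillule size is visible by design, because both sizes are set before every participant.

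**Working it through.** **Inputs from the document.** 90 mg of caffeine; 8 oz of water; 120 participants, 60 of them on caffeine; power 0.80. Thirty per cell is inferred from 120 participants in four groups.

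**Assumptions.** Two-sided alpha of 0.05, scores in SD units and the normal approximation. In addition:

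- d, the true size effect: 0.4 SD.
- p, the share of the caffeine groups who notice and then attribute nothing to the pillule: 0 to 0.75.
- q, the share of the plain-water groups who infer that they had no caffeine and then attribute nothing to the pillule: 0 to 0.75.
- e, the expectancy gain from noticing caffeine: 0.2 SD.

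**1. Concentration.** 8 × 29.57 mL = 236.6 mL, and 90 / 236.6 = 0.38 mg/mL. The document does not link this figure to a proportion who would notice.

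**2. The plan's own figure.** The total of 120 cannot be reproduced, because no effect size, SD or alpha is stated. Solving backwards for 60 v 60, the detectable main effect is (1.96 + 0.84) × √(2/60) = 0.51 SD. For the interaction, as a difference of differences with 30 per cell, it is (1.96 + 0.84) × √(4/30) = 1.02 SD.

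**3. Effect of the cue on hypotheses 2 and 3.** The size effect is (1 − q)d in the plain-water groups and (1 − p)d in the caffeine groups. Hence:

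- size main effect = d[1 − (p + q)/2], with standard error √(2/60) = 0.183;
- interaction bias (plain water minus caffeine) = (p − q)d, with standard error √(4/30) = 0.365.

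| p | q | Size main effect (SD) | Power for size | Interaction bias (SD) | Chance of declaring an interaction when there is no true one |
|---|---|---|---|---|---|
| 0 | 0 | 0.40 | 0.59 | 0 | 5% |
| 0.25 | 0 | 0.35 | 0.48 | 0.10 | 6% |
| 0.50 | 0 | 0.30 | 0.38 | 0.20 | 8.5% |
| 0.75 | 0 | 0.25 | 0.28 | 0.30 | 13% |
| 0.50 | 0.50 | 0.20 | 0.20 | 0 | 5% |
| 0.25 | 0.50 | 0.25 | 0.28 | −0.10 | 6% |

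The first four rows show the bias growing with p when plain water tells participants nothing. The last two show that it can vanish or reverse when plain water is informative too, while the dilution of the size effect gets worse.

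If d is instead 0.51 SD, the effect with 80% power, then with q = 0 the power for size falls from 0.80 to 0.69, 0.56 and 0.42 at p = 0.25, 0.50 and 0.75.

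**4. Effect on hypothesis 1.** The caffeine contrast shifts by p × e: 0.25 × 0.2 = 0.05 SD up to 0.75 × 0.2 = 0.15 SD, and zero at p = 0. With no true drug effect, shifts of 0.05 to 0.15 SD raise the false-positive rate from 5% to about 6% to 13%.

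**The case against.** The strongest case on the other side has four parts.

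**Detectability is not documented.** The text never says that caffeine is bitter and gives no taste threshold. This stands: p is unknown, zero cannot be excluded, and every magnitude above is an illustration.

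**The mechanism depends on what participants are told.** If they are told that the water may contain caffeine, the drink may be credited in all four groups whatever it tastes of. If they are led to think that the pillule is active, an odd taste may be put down to the pillule. This also stands, and it limits what can be said about size and direction. It does not make the two drinks alike.

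**The cue need not act in the caffeine groups only.** A reader might infer that taste weakens the pillule expectancy only where caffeine is given, so that it must create an interaction of p × d in a known direction. The documents do not support this. Participants can know that caffeine is involved, and tasteless water may tell some of them that they had none. With q above zero the bias is (p − q)d, of unknown sign.

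**A false interaction would seldom be declared.** Biases of 0.10 to 0.30 SD would be significant only about 6% to 13% of the time, since the detectable interaction is about 1.02 SD. This stands too. The estimate would still be biased, and the dilution of the size effect does not depend on that point.

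**Conclusion.** The concern holds as a design weakness that should be corrected before the first session. The document establishes the mismatch: caffeine in plain distilled water against plain distilled water, with nothing to match the taste and no record of what participants believe they had. The drink can therefore reveal the caffeine factor. The document does not show that it will.

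If some participants notice, hypothesis 1 mixes drug with awareness of drug, hypothesis 2 may be diluted, and hypothesis 3 may be biased by (p − q)d in an unknown direction. Under the assumptions stated, with q = 0 and p from 0 to 0.75, the size effect falls from 0.40 to as little as 0.25 SD, the interaction bias runs from 0 to 0.30 SD, and the caffeine contrast shifts by 0 to 0.15 SD. These figures rest on assumed p, q, d and e, and on noticing removing the whole size effect. Confidence is high in the mismatch and moderate at most in its consequences.

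**What to change.** In the Procedure:

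1. Give all four groups the same taste-masking, caffeine-free drink, in the same volume and in the same opaque cup. For the caffeine groups, dissolve the unchanged caffeine packet in it.
2. Before the first session, check that the two versions cannot be told apart. Tasters who do not know which version they have give a stronger check than the people who mixed it.
3. Before debriefing, ask each participant whether they think they received caffeine and, if so, whether it was in the drink or the pillule. Report the answers by group. They describe how far beliefs differ between groups, though a guess made after testing can also reflect felt effects of the drug.
4. State who is masked to the drink and what participants are told about the drink and the pillule.

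The cost is a small amount of flavouring, a short check, one or two questions per participant and a few protocol sentences. Dose, groups, tests and sample size do not change. The downside is that a flavoured drink is more noticeable than water and may draw some expectation away from the pillule, but equally in all four groups. Without the change, the confounding cannot be repaired once the data are collected.

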Caffeine may be a good option for testing this phenomenon for three reasons: 1) previous research already supports caffeine's improvements to cognitive functioning (EFSA, 2011); 2) caffeine use among college students is very salient, given the prominence of the caffeine across various products like energy drinks (Pettit & DeBarr, 2011); 3) using self-report measures to collect data on weekly caffeine consumption habits will allow adjustments for tolerance effects (Beaumont, et al., 2017;2016). Research on caffeine use in healthy adults has already shown significant improvement to memory, executive functioning, and processing speed (EFSA, 2011). Caffeine lends itself well to a randomized controlled trial design, allowing the introduction of tablet size as an additional factor. Previous research supports an increase in cognitive functioning after consuming caffeine; memory, executive functioning, and processing speed are improved after consuming caffeine (EFSA, 2011). The European Food and Safety Administration conducted a meta-analysis that assessed the different claims associated with consuming caffeine like increased fat oxidation, increased energy expenditure, increased

alertness, and increased attention. Their findings suggest that there is not enough data to support causal claims for caffeine causing increased fat oxidation and increased energy expenditure. However, a causal relationship between caffeine and increased alertness and increased attention is supported (EFSA, 2011). Pettit and Debarr conducted a study analyzing the association between stress and energy drink consumption, and the association between energy drink consumption and GPA in 136 college students ages 18-24 (Pettit & DeBarr, 2011). Their results show a positive correlation between perceived stress and energy drink consumption, and a negative correlation between GPA and energy drink consumption. However, the results in Pettit and DeBarr's study did not account for consumption of caffeine from other sources (e.g. coffee, tea, supplements, etc.). Heavy marketing for caffeinated products make caffeine an ideal substance to use for assessments when working with college students.

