Primary analysis will be done through a series of ANCOVAs, if a preliminary correlation analysis shows a significant relationship between weekly caffeine consumption and scoring for each cognitive component. If the preliminary correlation analysis does not show a significant relationship between weekly caffeine consumption and scores for each cognitive component, then a series of ANOVAs will be performed.

Proposed Timeline

Pending the approval of clinicaltrials.gov, materials will be gathered and prepared in early October. The UROP has been awarded and funds will be available once PRS has approved of this proposal. Recruitment will begin during the Fall semester. Recruitment and trials are expected to continue in through December and conclude as late as February. Course load will be kept to a minimum to allot enough time for trials every weekday during the morning.

[figure not shown]
15

Weekly caffeine consumption will be calculated for each participant from their reported

caffeine consumption habits (Appendix E).

	No caffeine	90 mg caffeine
Small tablet (1 mm diameter)	Average score on cogitive test	Average score on cognitive test
Large tablet (5 mm diameter)	Average score on cognitive test	Average score on cognitive test

Figure 1. Overall study design

The Effect of Tablet Size on Cognitive Performance: A RCT Using Caffeine

Figure 2. CONSORT diagram

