Appendix E

Questionnaire to Collect Weekly Caffeine Consumption

Subject ID _____ DAY 1

Date_____

CAFFEINE CONSUMPTION DIARY (CCD)

Please answer the following questions as completely and honestly as you can. This information is STRICTLY CONFIDENTIAL – do not write your name anywhere on this page. Thank you for your cooperation.

Log all item that you consume each day. Pay close attention to the size (in oz) of each product. For example, if you drink 10 oz of coffee this would count for 2 servings

(5 oz servings) 6am-12nn 12nn-6pm 6pm-2am 2am-6am Regular brewed	COFFEE	MORNING	AFTERNOON	EVENING	NIGHT
Percolated	(5 oz servings)	6am-12nn	12nn-6pm	6pm-2am	2am-6am
Percolated			^	^	
Drip-brewed					
Espresso shot	Percolated				
Regular instant	Drip-brewed				
Regular instant	Espresso shot				
Decaffeinated Brewed Instant	Regular instant				
Instant					
TEA (5 oz serv)	Brewed				
(5 oz serv)	Instant				
(5 oz serv)					
COCOA (5 oz serv)	TEA				
(5 oz serv) MORNING AFTERNOON EVENING NIGHT (2 oz serv) 6am-12nn 12nn-6pm 6pm-2am 2am-6am Diet Coca-Cola	(5 oz serv)				
CHOCOLATE (8 oz serv) MORNING 6am-12nn AFTERNOON 12nn-6pm EVENING 6pm-2am NIGHT 2am-6am Diet Coca-Cola [name]	COCOA				
(8 oz serv) MORNING 6am-12nn AFTERNOON 12nn-6pm EVENING 6pm-2am NIGHT 2am-6am Coca-Cola	(5 oz serv)				
SOFT DRINKS (12 Oz. Serv) MORNING 6am-12nn AFTERNOON 12nn-6pm EVENING 6pm-2am NIGHT 2am-6am Diet Coca-Cola Diet Coca-Cola [name]	CHOCOLATE				
(12 Oz. Serv) 6am-12nn 12nn-6pm 6pm-2am 2am-6am Diet Coca-Cola	(8 oz serv)				
(12 Oz. Serv) 6am-12nn 12nn-6pm 6pm-2am 2am-6am Diet Coca-Cola	SOFT DRINKS	MORNING	AFTERNOON	EVENING	NIGHT
Coca-Cola	(12 Oz. Serv)				2am-6am
Diet Coca-Cola					
[name]					
Diet [name]					
Mountain Dew	[name]				
Diet Mountain Dew					
[name]					
Diet [name]					
Tab					
Pepsi Cola					
Diet Pepsi Cola					
RC Cola					
Mello Yello					
Diet Mello Yello Root Beer Red Bull					
Root Beer Red Bull					
Red Bull					
OVER-THE-COUNTER					
DRUGS (Tablets) Vivarin NoDoz Excedrin Vanquish Anacin Dristan	Red Bull				
DRUGS (Tablets) Vivarin NoDoz Excedrin Vanquish Anacin Dristan	OVER THE COUNTER				
(Tablets) Vivarin NoDoz					
NoDoz					
Excedrin					
Vanquish Anacin					
Anacin Dristan					
Dristan					
Dexatrim					
	Dexatrim				

Adapted from the CCQ by R.E. Landrum 1988

Participants will be asked to fill in 7 sheets, one for each day of the week.

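### Weekly caffeine intake, the one named covariate, is reported after the study drink; collecting it before dosing would rule out a possible but unproven bias in the adjusted caffeine effect

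*Combined protocol and SAP*

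**What the plan says.** The session is described twice, and the descriptions differ on when intake is reported.

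- **Abstract:** "Participants will consume the designated placebo tablet with water (caffeinated or non-caffeinated); then, participants will provide weekly caffeine intake". This falls in the waiting period before any cognitive test.
- **Method, Procedure:** the drink, the 30-minute wait, the three Stroop tests and RAVLT immediate recall come first. Then, in the RAVLT delay, "participants will complete Trail Making Tasks A and B, and fill out a demographic survey designed to collect: 1) their weekly caffeine intake". If time runs out, "the survey materials will be set aside and completed after participants finish the second component of the RAVLT".

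Neither description collects intake before the drink, and nor does any other section.

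Appendix E is laid out as a daily diary: "Participants will be asked to fill in 7 sheets, one for each day of the week". Data Analysis gives the variable its role: "Primary analysis will be done through a series of ANCOVAs, if a preliminary correlation analysis shows a significant relationship between weekly caffeine consumption" and the scores; otherwise ANOVAs are used. The introduction gives the purpose: "using self-report measures to collect data on weekly caffeine consumption habits will allow adjustments for tolerance effects". It adds that scores left unadjusted for habitual intake could be confounded.

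**The concern.** ANCOVA estimates the treatment effect without bias when treatment cannot affect the covariate. A value recorded before dosing meets that condition by design. A value reported after dosing meets it only if the report is unaffected by the drink.

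The plan leaves some room for an effect. The first hypothesis is that "caffeine will significantly improve participant's memory, executive function, and processing speed", and a seven-day report completed within the session appears to rest on memory. Under the catch-up rule, the time at which the form is completed also depends on how quickly the participant works, and the same hypothesis says caffeine changes that. If mean reported intake came to differ between the caffeine and no-caffeine groups, adjustment would move the estimated caffeine effect by an amount unrelated to cognition, and the test would no longer have its nominal error rate. The same could happen to the tablet-size and interaction effects if tablet size altered reporting.

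**Working it through.** **1. Timing.** Both descriptions are post-dose. Appendix A says sixty statements are shown at one every thirty seconds: 60 × 0.5 min = 30 min. The mood task therefore fills the wait, which suggests that the Procedure is the working version and leaves no obvious time for the Abstract's placement.

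**2. The plan's own figure.** The Procedure gives 120 participants at 0.80 power, without effect size, SD, alpha or sidedness, so 120 cannot be reproduced, only solved backwards. Assuming two-sided 0.05 and 60 against 60 on the caffeine factor:

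d = (1.960 + 0.842) × √(2/60) = 2.802 × 0.1826 = 0.511 SD.

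This serves below as a yardstick.

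**3. When ANCOVA is chosen.** With n = 120 and two-sided 0.05 (assumed), the correlation is significant when

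|r| ≥ t/√(t² + 118), with t = 1.980, which gives 0.179.

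**4. Size of the bias.** Let r be the within-group correlation of reported intake with the score, and dX the caffeine-induced shift in mean reported intake, in SD. Neither is in the documents; both are assumed over a range. For a linear ANCOVA:

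- bias = −r × dX (in within-group outcome SD)
- SE = √(1 − r²) × √(2/60) × √(1 + dX²/4)
- type I error = 1 − Φ(1.96 − |bias|/SE) + Φ(−1.96 − |bias|/SE)

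Example, r = 0.3 and dX = 0.2: bias = 0.06; SE = 0.954 × 0.1826 × 1.005 = 0.175; ratio = 0.343; type I error = 0.064.

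| r | dX | Absolute bias (SD) | Type I error |
|---|---|---|---|
| any | 0 | 0 | 0.050 |
| 0.2 | 0.1 | 0.02 | 0.051 |
| 0.4 | 0.1 | 0.04 | 0.057 |
| 0.3 | 0.2 | 0.06 | 0.064 |
| 0.3 | 0.5 | 0.15 | 0.133 |
| 0.4 | 0.5 | 0.20 | 0.213 |

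Simulation agreed: at r = 0.3, dX = 0.2 it gave a bias of −0.062 and type I error of 0.065 over 6,000 runs. At r = 0.4, dX = 0.5 simulated type I error was 20.1% over 5,000 runs.

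**5. Effect of the correlation rule.** Letting the rule choose between ANCOVA and ANOVA gave −0.058 and 0.064 at r = 0.3, dX = 0.2, nearly the same. At r = 0.2 the rule selects ANCOVA only about 60% of the time; with dX = 0.2 the average bias fell from 0.038 to 0.028 SD, with type I error of 5.4%.

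**6. Effect on power.** At a true effect of 0.511 SD and r = 0.3, power is 0.835 when dX = 0. At dX = 0.2 it is 0.73 if the bias opposes the effect and 0.90 if it adds to it. The 0.06 SD bias is 0.06/0.511 = 12% of the yardstick.

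**The case against.** The strongest reply is that the quantity of interest, intake over past days, is fixed before randomisation. The drink cannot alter it; only the report can move, and no section of the plan supports a shift of any size. At dX = 0.1 type I error stays close to nominal. This stands, and it limits the point to a safeguard.

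Four further objections also have force.

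- **The memory route is indirect.** The plan tests memory with words learned after dosing. The questionnaire concerns drinks taken before dosing, so only retrieval could be affected, and better retrieval need not move mean reported intake in one direction.
- **Recall is an inference.** Appendix E is headed a diary and asks for daily logging. Completion from memory is the likeliest reading of the Procedure, but the plan does not say so.
- **The correlation rule does not make matters worse.** A reader might infer that it picks out the cases of greatest bias. Averaged over trials, it slightly reduces the bias.
- **Moving the form has a cost.** The Procedure already allows for the survey not fitting into the RAVLT delay. Seven caffeine sheets just before the drink would also prime expectancy in a trial about expectancy.

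What remains is that the trial could not show afterwards that dX was zero. With 60 per group, a comparison of reported intake has a standard error of √(2/60) = 0.183 SD. A true shift of 0.2 SD gives a ratio of 0.2/0.183 = 1.10 and power of only about 0.19, so a null comparison would offer little reassurance.

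**Conclusion.** The point holds as a safeguard against a possible bias. The post-dose timing and the disagreement between Abstract and Procedure are plain in the text. The bias is conditional: about r × dX SD, zero when dX = 0, 0.02 to 0.04 SD with near-nominal error at dX = 0.1 (r from 0.2 to 0.4), and 0.06 SD with type I error of about 6.4% at r = 0.3, dX = 0.2. These figures assume a linear ANCOVA, 60 per caffeine group, two-sided 0.05 and no dropout. The bias arises only for outcomes where the correlation rule selects ANCOVA, and its direction is unknown.

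A reader might infer that the primary analysis is biased, or that its false-positive rate is about 20%. The documents support neither. The 20% belongs only to the corner r = 0.4, dX = 0.5, and nothing in the plan suggests a shift that large. Nor does the hypothesis that caffeine improves memory establish that it changes mean reported intake.

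**What to change.** 1. Collect Appendix E before dosing. The preferred way is to hand out the seven sheets at sign-up and have one completed on each day of the week before the session, as the form is written. Completing all seven just before the drink is the weaker option: it lengthens the session and primes caffeine expectancy more directly.
2. State in Data Analysis that only this pre-dose value enters the preliminary correlation and the ANCOVA.
3. Make the Abstract and Procedure give the same timing. Moving the form to the end of the session would not help, because it would still be post-dose.
4. If the form must stay post-dose, make the unadjusted ANOVA primary and report intake by group, noting that 60 per group could easily miss a modest shift.

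The cost is a contact and hand-out a week ahead, some sheets not returned, and some caffeine priming. The priming should be equal across the four groups, although equal priming does not exclude some change in the tablet-size effect. The sample size stays at 120. With dX = 0 by design, the bias is zero and type I error 0.05; power at 0.511 SD is about 0.81 at r = 0.18 and 0.84 at r = 0.3.
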